
Efficacy: Efficacy endpoints will include the following:
 
 • Evaluate the exhaled $^{13}\text{CO}_2$ levels at each time point post-nebulization • Evaluate the relationship between the exhaled $^{13}\text{CO}_2$ levels at each time point and subject's causative pathogen based upon sputum culture or NGS • Evaluate the sensitivity and specificity of the ^{13}C-urea breath test for urease producing pathogens • Evaluate the positive and negative predictive value of the ^{13}C-urea breath test for urease producing pathogens • Correlation of the ^{13}C-urea breath test with CURB65 in subjects with sputum cultures positive for urease pathogens • Correlation of the ^{13}C-urea breath test with PSI in patients with sputum cultures positive for urease pathogens • Univariate association of all study variables with urease pathogen caused pneumonia • Multi-variate logistic regression model for urease pathogen caused pneumonia utilizing study variables that are significant in univariate analysis to compute odds ratio for each model variable and overall explanation of variance by model 	

Safety: Safety endpoints will include:
 
 • Incidence of adverse events (AEs) • Incidence of death, transfer to ICU, or intubation 	

SYNOPSIS (PAGE 4 OF 4)

Name of Sponsor/Company: [name], PhD University of New Mexico	Protocol Number: 16-327
Name of Study Drug/Device: ^{13}C -Urea solution for nebulization	Protocol Title: A Phase 1, open-label, evaluation of a ^{13}C -urea breath test for the detection of urease-producing bacteria in patients with pneumonia in the emergency department.
Name of Active Ingredient: ^{13}C -urea	Phase of Development: 1
Statistical methods:	
Sample size determination: The sample size for this study was selected based on prior exposures and existing safety data. Descriptive statistical analysis of results are planned as findings from this study will be used in order to appropriately determine the sample size requirements for future definitive evaluations of inhaled ^{13}C -urea in an adequately powered study of efficacy in this population.	

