2. STUDY OBJECTIVE

The primary objective of this study is to determine the ability of the ¹³C-urea breath test to detect urease producing pathogens in patients with pneumonia as confirmed on sputum culture results.

Additional objectives of this study will include:

- Determine optimal times for post-nebulization breath collection
- Evaluate the safety and tolerability of the ¹³C-urea breath test in patients with pneumonia

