6.3. Safety Assessments Description

6.3.1. Clinical Laboratory Tests

During screening, subjects will have samples collected for testing as follows:

Sputum:

- Bacterial culture (only required for Cohort B)

Urine

- Pregnancy test (female subjects)

Laboratory tests do not need to be repeated if samples have already been collected as part of the presenting or admission workup for the current ED visit or hospitalization.

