9.2. Study Endpoints

9.2.1. Efficacy Endpoints

Efficacy endpoints will include the following:

- Evaluate the exhaled ¹³CO₂ levels at each time point post-nebulization
- Evaluate the relationship between the exhaled ¹³CO₂ levels at each time point and subject's causative pathogen based upon sputum culture or NGS analysis
- Evaluate the sensitivity and specificity of the ¹³C-urea breath test for urease producing pathogens
- Evaluate the positive and negative predictive value of the ¹³C-urea breath test for urease producing pathogens
- Correlation of the ¹³C-urea breath test with CURB65 in subjects with sputum cultures or NGS results positive for urease pathogens
- Correlation of the ¹³C-urea breath test with PSI in patients with sputum cultures or NGS results positive for urease pathogens
- Univariate association of all study variables with urease pathogen caused pneumonia
- Multi-variate logistic regression model for urease pathogen caused pneumonia utilizing study variables that are significant in univariate analysis to compute odds ratio for each model variable and overall explanation of variance by model

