9.5. Efficacy Analysis

Breath test exhaled $^{13}\text{CO}_2$ results at each time point will be presented for the overall population for determination of optimal breath sampling time. Relationship between the exhaled $^{13}\text{CO}_2$ at each time and subject's pneumonia diagnosis and pathogen (determined by sputum culture) will be examined. The time point where exhaled $^{13}\text{CO}_2$ can reliably predict the presence of urease positive pathogen in subjects with pneumonia diagnosis will be considered as the optimal time for ^{13}C -urea breath test sampling.

The proportion of subjects with breath test positive/negative determination will be compared to sputum culture results when available. Correlation analyses will be performed where sufficient data are available.

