APPENDIX A. SCHEDULES OF STUDY VISITS AND PROCEDURES

Table 1: Schedule of Study Procedures

Procedure	Screening	Treatment			Follow-Up 48 Hours Post Breath Test
		Pre-Treatment	Nebulization	0-10 Minutes Post-Nebulization	
Informed Consent	X				
Inclusion/Exclusion Evaluation	X				
Demographics and Medical History	X				
Physical Examination	X				
Sputum Collection	X ^b				
Oropharyngeal Swab	X ^b				
Urine Pregnancy Test	X				
Breath Sample Collection		X ^a		X ^a	
Vital Signs	X	X	X	X	
¹³ C-urea Administration			X		
Safety Contact					X
Prior and Concomitant Medication	<----- X ----->				
Adverse Event Monitoring			<----- X ----->		

a Up to 6 samples collected pre- and post-nebulization

b Only required for Cohort B

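### The logistic model keeps whichever variables pass a univariate test and reports explained variance from the same subjects without validation, so that figure will be too high

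*Combined protocol and SAP*

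**What the plan says.** The last two efficacy endpoints in 9.2.1 work as a pair. The first is "Univariate association of all study variables with urease pathogen caused pneumonia". The second is a multivariable logistic model for the same outcome, "utilizing study variables that are significant in univariate analysis to compute odds ratio for each model variable and overall explanation of variance by model". The synopsis repeats it: "Multi-variate logistic regression model for urease pathogen caused pneumonia utilizing study variables that are significant in univariate analysis". The documents give no candidate list, no cap on the number of variables, no threshold for significance and no type of R². Section 9.5 does not mention the model. Nothing in the text supplied provides for a bootstrap, cross-validation, a hold-out sample or shrinkage.

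For the reference standard, 9.2.1 speaks of the "causative pathogen based upon sputum culture or NGS analysis", while 9.5 names culture only. In Appendix A, Table 1, sputum collection and the oropharyngeal swab both carry the footnote "Only required for Cohort B", and 6.3.1 limits culture in the same way.

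The sampling time is also to be chosen from the data. Section 2 has the objective "Determine optimal times for post-nebulization breath collection", and 9.5 takes the time at which exhaled ¹³CO₂ "can reliably predict the presence of urease positive pathogen in subjects with pneumonia diagnosis will be considered as the optimal time".

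Section 9.1 calls the analysis descriptive. Section 9.3.2 disclaims formal hypotheses and reports nominal p-values. Section 9.3.3 imputes nothing except missing adverse event ratings.

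**The concern.** A variable passes a univariate screen partly because it is related to the outcome and partly by chance in that sample. If the survivors are then fitted to the same subjects, the chance part is counted as explained variance. The fewer the outcome events per candidate, the larger that part. Here the candidate pool is open-ended and the number of urease-positive subjects may be small.

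Explained variance is a named efficacy endpoint. A reader who sees an R² near 0.4 has no signal that the same model might explain half of that, or nothing, in new subjects.

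**Working it through.** The plan has no figure of its own to reproduce: the sample size is not derived from statistical inputs.

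**1. Subjects.** Section 3.1 gives up to 75 subjects, 15 of them in Cohort A: 75 − 15 = 60 with a required reference sample. Optional Cohort A cultures could add a few. Missing data would remove some.

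**2. Candidates.** Counted from the documents: 9 in 6.2.1 (demographics, body size, two severity scores), 6 in 6.2.2 (tobacco, four healthcare-exposure items, chest x-ray), 6 vital signs in 6.3.2 (blood pressure as two), prior antibiotics from the medication record (5.10) and one breath measure: 9 + 6 + 6 + 1 + 1 = 23. This is one reasonable list, not the plan's. Events per candidate at 6, 12, 18 and 24 positives: 6/23 = 0.26, 12/23 = 0.52, 18/23 = 0.78, 24/23 = 1.04.

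**3. Chance entry.** With k independent noise variables screened at 0.05, P(at least one enters) = 1 − 0.95^k: 0.40 for k = 10, 0.64 for k = 20, 0.79 for k = 30.

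**4. Simulation of the rule.** Assumed: n = 60; 23 candidates; 0.05 screen; maximum-likelihood logistic fit of all that pass; Nagelkerke R² = [1 − (L0/L1)^(2/n)] / [1 − L0^(2/n)]. The breath measure, where predictive, is shifted by 1.19 SD, so AUC = Φ(1.19/√2) = 0.80 and the true odds ratio is exp(1.19) = 3.29 per SD. New-subject R² applies the fitted model to fresh simulated subjects and can be negative. Setting A has dependent candidates, 10 of them binary (1000 runs per cell), with a separately coded repeat of 400 runs. Setting B has independent candidates. Medians by number of positives:

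| Quantity | 6 | 12 | 18 | 24 |
|---|---|---|---|---|
| Nothing predictive: a non-breath noise variable enters (A) | 53% | 56% | 55% | 58% |
| Nothing predictive: apparent R² when a model is built (A) | 0.23 | 0.18 | 0.16 | 0.15 |
| Nothing predictive: apparent R², no-model runs as 0 (A) | 0.14 | 0.11 | 0.10 | 0.10 |
| Nothing predictive: apparent R², no-model runs as 0 (B) | 0.17 | 0.13 | 0.12 | 0.11 |
| Breath only: apparent R² (A) | 0.36 | 0.38 | 0.41 | 0.42 |
| Breath only: new subjects (A) | 0.00 | 0.19 | 0.22 | 0.25 |
| Breath only: apparent R² (A, repeat) | 0.33 | 0.38 | 0.40 | 0.41 |
| Breath only: new subjects (A, repeat) | 0.00 | 0.19 | 0.22 | 0.26 |
| Breath only: apparent R² (B) | 0.41 | 0.41 | 0.42 | 0.43 |
| Breath only: new subjects (B) | −0.06 | 0.14 | 0.21 | 0.22 |

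With 12 or more positives the gap between medians runs from 0.41 − 0.26 = 0.15 to 0.41 − 0.14 = 0.27. At 6 positives it runs from 0.33 − 0.00 = 0.33 to 0.41 + 0.06 = 0.47.

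**5. Sensitivity.**
- If NGS raised the positives to 30 of 60: 0.42 apparent, 0.29 in new subjects.
- If n = 75 with 8/15/30 positives: 0.34/0.38/0.41 apparent, 0.07/0.18/0.27 in new subjects.
- With two further real predictors (setting B): 0.55/0.58/0.60/0.61 apparent, −0.09/0.25/0.30/0.38 in new subjects.
- A separate grid used n of 60 or 75, 15%, 25% or 40% positive, 10, 20 or 30 independent candidates, and either no predictor or one with log odds ratio 1 per SD. Apparent R² exceeded new-subject R² in all 36 settings. With a real predictor the smallest gap was 0.11 (mean apparent against median new-subject).
- Cox-Snell R² gives smaller figures: about 0.11 when a model is built and nothing predicts.

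**6. Odds ratio for breath (A).** Screened model: 4.4/3.7/3.7/3.6 against a true 3.29, so clearly inflated only at about 6 positives.

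**The case against.** The strongest reply is that this is the last of eight efficacy bullets in a descriptive Phase 1 study with openly unadjusted p-values, and that the plan nowhere presents the R² as predictive performance. That limits the weight of the point. It does not remove it: a warning about p-values tells the reader nothing about an R² that was selected and fitted on the same subjects.

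A reader might infer that the screened model predicts worse than the breath measure alone. In the breath-only runs it does (at 24 positives, 0.25 against 0.31 in new subjects), but there every other candidate is noise, so adding one can only hurt. The protocol collects healthcare-exposure items and tobacco use, and nothing in it says they are uninformative. With two real clinical predictors at an assumed 0.8 SD shift, screened against breath alone in new subjects is 0.03 against 0.21 at 6 positives, 0.25 against 0.28 at 12, 0.36 against 0.32 at 18 and 0.42 against 0.34 at 24. The ranking depends on facts that the documents do not give.

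The candidate count is also open to challenge. Chest x-ray is nearly constant in Cohort B, where positive imaging is an entry criterion. Routine laboratory results (6.2.3) and the other breath times are left out and would raise the count. Section 5.10 does not name antibiotics. The percentages move with the list; the direction does not.

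Finally, replacing the screen with breath alone would drop the adjusted odds ratios that 9.2.1 asks for. That is a fair objection, so the remedy should remain multivariable where the number of positives allows.

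**Conclusion.** The point holds: followed as written, the rule yields an explained variance that is too high. The size rests on assumed prevalence, a 0.05 screen, Nagelkerke R², an assumed breath AUC and a candidate list drawn up for this check. The direction was the same in every setting tried.

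The issue is minor to moderate. Sensitivity, specificity, positive and negative predictive value and the primary objective do not pass through this model. A reader might also infer that future studies will be sized from the inflated R². Section 9.1 says that findings will inform later sample sizes but does not name this model, so the documents do not support that. Nor do they support a general claim that the breath odds ratio is inflated.

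**What to change.** In 9.2.1 and 9.5:

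- Keep the univariate associations as a descriptive table with confidence intervals, and stop using them to choose model variables.
- Pre-specify a small multivariable model: one breath measure (¹³CO₂ change over baseline) plus one or two covariates already collected and named before analysis, for example one severity score and one healthcare-associated-pneumonia criterion. Section 6.2.1 makes the scores conditional on available data and 9.3.3 allows no imputation, so favour items likely to be complete. If positives are very few (about 6), fit breath alone.
- Fit by Firth penalised likelihood, state the R² type, and report bootstrap optimism-corrected R² and AUC beside the apparent values. Repeat any data-driven choice of sampling time inside each resample. Label the model exploratory.

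The correction was checked. For a small pre-specified multivariable Firth model with two further real predictors, corrected R² at 6/12/18/24 positives is 0.28/0.37/0.43/0.46 against 0.27/0.43/0.45/0.48 in new subjects. For breath alone with the best of six times chosen inside each resample, at 6/12/24 positives, apparent R² is 0.26/0.31/0.38, corrected 0.14/0.24/0.32 and new-subject 0.18/0.25/0.31. The correction is therefore compatible with the optimal-time objective.

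If the sponsor keeps the screen, state its threshold, label the apparent R² as optimistic, and report the corrected AUC from resampling that repeats the screen: 0.77/0.75/0.76 against 0.75/0.77/0.79 in new subjects (apparent 0.87/0.84/0.83). Do not rely on the bootstrap-corrected R² of the screened model, which over-corrects: −0.52/−0.30/−0.13 against 0.00/0.16/0.28.

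The cost is SAP wording and routine software. The downside is fewer adjusted odds ratios than the screen might give, a less favourable explained-variance figure and a little more analysis work. Enrolment, samples and conduct do not change.

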9.2.2. Safety Endpoints

Safety endpoints will include the following:

- Incidence of all AEs
- Incidence of death, transfer to ICU, or intubation

9.3. General Considerations for Statistical Analysis

9.3.1. Analysis Datasets

Intent-to-Treat (ITT) Analysis Set: The ITT set will include all subjects who receive nebulized ¹³C-urea. The ITT set is also referenced as the Safety analysis set. All safety analysis will be based on the ITT analysis set.

Modified Intent-to-Treat (mITT) Analysis Set: The mITT subjects include all ITT subjects who provide at least one post-dose breath sample. The mITT analysis set will be used for efficacy analysis.

9.3.2. Test Hypothesis and *P* Value Justification

No formal statistical hypothesis will be examined. When a p-value is produced from an analysis, the nominal p-value will be reported as is without adjustment for multiplicity.

9.3.3. Procedures for Handling Missing Data

Unless indicated otherwise, no imputation will be done for missing data. However, AEs with missing severity assessments will be tabulated as “severe,” and AEs with missing relationship assessments will be tabulated as “related” for the purpose of analysis; and the missing data will be presented in data listing as is.

9.4. Study Population Summaries

Population summaries will be provided for the safety analysis set included in this study.

9.4.1. Disposition

The summary tables will provide frequency counts for subject disposition (all treated subjects, subjects who completed the study, subjects who discontinued from the study, and reason for discontinuation) for the study overall and for each cohort. Identification numbers for discontinued subjects will also be included in the tables.

Disposition in terms of number of subjects excluded from each analysis sets (ITT and mITT) will also be provided for the overall population and for each cohort.

9.4.2. Demographics

The demographic summary will include descriptive statistics for age, sex, race, weight, height, and BMI for the overall study population.

9.4.3. Protocol Violations

All protocol violations and deviations will be identified.

9.4.4. Treatment Compliance

All doses of study medication will be overseen by study personnel. The exact time of initiation and completion of nebulization will be documented within each subject’s CRF. No formal summary of treatment compliance will be produced.

9.4.5. Prior and Concomitant Medications

All prior and concomitant medications will be tabulated for the overall study population. Prior and concomitant medications will be coded to the therapeutic drug classes and generic drug names using the World Health Organization (WHO) Drug classifications version 1Q2015 or higher.

9.5. Efficacy Analysis

Breath test exhaled $^{13}\text{CO}_2$ results at each time point will be presented for the overall population for determination of optimal breath sampling time. Relationship between the exhaled $^{13}\text{CO}_2$ at each time and subject's pneumonia diagnosis and pathogen (determined by sputum culture) will be examined. The time point where exhaled $^{13}\text{CO}_2$ can reliably predict the presence of urease positive pathogen in subjects with pneumonia diagnosis will be considered as the optimal time for ^{13}C -urea breath test sampling.

The proportion of subjects with breath test positive/negative determination will be compared to sputum culture results when available. Correlation analyses will be performed where sufficient data are available.

9.6. Safety and Tolerability Evaluations

All analyses will be provided for the overall group.

9.6.1. Extent of Exposure

All subjects will receive Study drug ^{13}C -urea solution via Aerogen Aeroneb Solo nebulizer device. The solution will be nebulized until the full dose has been administered, with subjects breathing normally through their mouths using the nebulizer mouthpiece.

No formal exposure summary will be prepared.

9.6.2. Adverse Events

The Medical Dictionary for Regulatory Activities (Version 18 or higher) will be used to classify all AEs with respect to system organ class and preferred term.

Three types of summaries will be produced for the AE summary:

1. an overall summary of AEs: number of subjects with at least one event and number of events for each severity for all AEs, and SAEs
2. a summary table of AEs and SAEs by system organ class and preferred term and severity
3. a summary table of AEs and SAEs by preferred terms in descending order of total incidence

AEs will be tabulated by cohort and for study overall. AEs that lead to premature discontinuation from the study or to death will be listed separately via data listings.

9.6.3. Clinical Laboratory Tests

The study will not have routine clinical safety laboratory tests. Bacterial culture results will be summarized for the study overall.

9.6.4. Subgroup Analyses for Safety Endpoints

No subgroup analysis is planned for safety endpoints.

9.7. Interim Evaluation

No interim analysis is planned for this study.

10. STUDY ADMINISTRATION

10.1. Regulatory and Ethical Considerations

10.1.1. Regulatory Authority Approval

The investigator will obtain approval to conduct the study from the appropriate regulatory agency in accordance with any applicable country specific regulatory requirements before any site may initiate the study in that country.

10.1.2. Ethical Conduct of the Study and Ethics Approval

This study will be conducted according to GCP; US 21 Code of Federal Regulations (CFR) Part 50 (Protection of Human Subjects); US 21 CFR Part 56 (IRBs); US 21 CFR Part 54 (Financial Disclosure); International Conference on Harmonization (ICH) Guidance for Industry, E6 GCP: Consolidated Guidance; the Nuremberg Code; and, where applicable, the principles of the Declaration of Helsinki (Recommendations guiding Medical Doctors in Biomedical Research Involving Human Subjects).

10.1.2.1. Ethics Committees

The investigator is responsible for ensuring that this protocol, the site's informed consent form, and any other information that will be presented to potential subjects (e.g., advertisements or information that supports or supplements the informed consent form) are reviewed and approved by the appropriate IRB or IEC. The investigator agrees to allow the IRB or IEC direct access to all relevant documents. The IRB or IEC must be constituted in accordance with all applicable regulatory requirements.

If the protocol, the informed consent form, or any other information that the IRB or IEC has approved for presentation to potential subjects is amended during the study, the investigator is responsible for ensuring that the IRB or IEC reviews and approves, where applicable, these amended documents. The investigator must follow all applicable regulatory requirements pertaining to the use of an amended informed consent form, including obtaining IRB or IEC approval of the amended form, before new subjects consent to take part in the study using the new version of the form. IRB or IEC approval of the consent forms must be obtained in addition to the approval given for the clinical study. Regulatory review and approval may be required in some countries before IRB or IEC approval can be sought.

10.1.2.2. General Considerations

The ethical standards defined within GCP are intended to ensure the following:

- Human subjects are provided with an adequate understanding of the possible risks of their participation in the study, and they have a free choice to participate or not.
- The study is conducted with diligence and in conformance with the protocol in such a way as to ensure the integrity of the findings.
- The potential benefits of the research justify the risks.

10.1.3. Informed Consent

The informed consent form must reflect the required elements of informed consent specified in 21 CFR Part 50.25. The final informed consent form must be approved by the IRB or IEC. If any new information becomes available that might affect subjects' willingness to participate in the study, or if any amendments to the protocol require changes to the informed consent form, the IRB or IEC must provide written approval of any revisions to the informed consent form in advance of its use.

Consenting will occur according to GCP and clinical site practices in the emergency department or Clinical and Translational Science Center (adjacent to UNM-ED, Cohort A only).

Investigators must provide subjects with all the information necessary to make an informed decision about their participation in the study, including the nature and intended purpose of the study, possible benefits, and possible risks.

All information in the informed consent form should be provided in a language (whether written or spoken) that is as nontechnical as practical and that is understandable to the subjects.

Before written informed consent is obtained, the subject should be given ample time and opportunity to inquire about the details of the study. All questions must be answered to the satisfaction of the subject (or his or her legally authorized representative).

This study requires administration of nebulized urea within 4 hours of administration of antibiotics. Subjects will be told that if they wish to participate in the study, they will need to decide to participate within 3 hours of receiving antibiotics in the emergency department in order to participate in the study. The study procedures will not delay or interfere with antibiotic administration.

Before a subject undergoes procedures specific to the protocol, the informed consent form must be signed and dated by the subject (or his or her legally authorized representative) and any other signatories as required by the IRB or IEC.

If a subject (or legally authorized representative) cannot read, a short form approved by the IRB or IEC may be used. Only the short form itself is to be signed by the subject or the representative. However, the witness shall sign both the short form and a copy of the summary, and the person actually obtaining the consent shall sign the copy of the summary in accordance with 21 CFR 50.27 (b2).

After all required signatures have been obtained, a copy of the informed consent form should be provided to the subject, and the original must be kept on file at the site and made available for review. Documentation of the informed consent discussion must be noted in the subject's case history.

